14.3.3 Appendix 3: Sample Pharmacokinetic and EKG Worksheet for Mithramycin

14.3.3.1 Cycle 1*

TEL Research Sample # (2 10 mL red top tubes & 2 10 mL lavender top tubes)	Coag Reference Sample # (obtain kit from TEL)	PK Sample # (2.3 mL lavender top tubes)	Hour (pre dose = within 1 hour prior to infusion)	Target Time	Actual Time	EKG Time	Initials
C1D1	(date)						
R1	C 1	PK 1	pre dose				
n/a	n/a	PK 2	2h post start of infusion				
n/a	n/a	PK 3	8h post start of infusion				
n/a	n/a	PK 4	16h post start of infusion				
C1D2	n/a	PK 2	Just prior to the end of the 24 hour infusion				
n/a	n/a	PK 3	0.25h post-infusion				
n/a	n/a	PK 4	0.5h post infusion				
n/a	n/a	PK 5	1h post infusion				
n/a	n/a	PK 6	2h post infusion				
n/a	n/a	PK 7	3h post infusion				
n/a	n/a	PK 8	5h post infusion				
n/a	n/a	PK 9	7h post infusion				
n/a	n/a	PK 10	9-12h post infusion				
C1D4	(date)						
R2	n/a						

*Note: If a dose modification is implemented (Section 3.3), the patient's PKs at the start of the next treatment cycle may be collected starting with Cycle 1 Day 1 of the PK calendar (refer to Section 3.5.3).

14.3.3.2 Cycle 2

TEL Research Sample # (2 10 mL red top tubes & 2 10 mL lavender top tubes)	Coag Reference Sample # (obtain kit from TEL)	PK Sample # (2 3 mL lavender tubes)	Hour (pre dose = within 1 hour prior to infusion)	Target Time	Actual Time	EKG Time	Initials
C2D1	(date)						
R3	C 3	PK 1	pre dose				
C2D2	(date)	PK 2	Just prior to the end of the 24 hour				

14.3.3.3 Cycle 3

TEL Research Sample # (2 10 mL red top tubes & 2 10 mL lavender top tubes)	Coag Reference Sample # (obtain kit from TEL)	PK Sample # (2 3 mL lavender tubes)	Hour (pre dose = within 1 hour prior to infusion)	Target Time	Actual Time	EKG Time	Initials
C3D1	(date)						
R4	C 4	PK 1	pre dose				
C3D2	(date)	PK 2	Just prior to the end of the 24 hour				

14.3.3.4 Cycle 4

TEL Research Sample # (2 10 mL red top tubes & 2 10 mL lavender top tubes)	Coag Reference Sample # (obtain kit from TEL)	PK Sample # (2 3 mL lavender tubes)	Hour (pre dose = within 1 hour prior to infusion)	Target Time	Actual Time	EKG Time	Initials
C4D1	(date)						
R5	C 5	PK 1	pre dose				
C4D2	(date)	PK 2	Just prior to the end of the 24 hour				

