1 INTRODUCTION

1.1 STUDY OBJECTIVES

1.1.1 Primary Objectives

- To determine pharmacokinetics, toxicities, and maximum tolerated dose (MTD) of mithramycin administered as a continuous 24h infusion in patients with primary thoracic malignancies or carcinomas, sarcomas or germ cell tumors metastatic to the chest.
- To determine objective response rates (CR and PR) of mithramycin administered as 24h intravenous infusions in patients with primary malignancies involving lungs, esophagus, thymus, pleura, chest wall or mediastinum; or carcinomas, sarcomas or germ cell tumors metastatic to the chest following mithramycin infusions administered at the MTD.

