1.3.2.1 Pharmacokinetics

Administration of tritium labeled mithramycin to monkeys showed a terminal half-life of 5 hours. The peak cerebrospinal fluid concentration: plasma ratio was 0.12 and reached after 1 ½ hours (67). Preliminary pharmacokinetic parameters of ¹²⁵I-plicamycin (mithramycin) in human plasma using a radioimmunoassay were described (68). Three patients were studied and received mithramycin at a dose ranging from 0.85 to 1.0 mg/m² IV over 2 hours. Drug elimination was biphasic, with a mean elimination half-life of 10.6 hours (±1.7), and a clearance rate of 11.1 ±0.4 mL/min/m².

Kennedy et al (52) administered tritiated mithramycin by IV or IP routes in mice at doses closely approximating 2 mg/kg. Blood, liver, and kidney mithramycin concentrations following IP administration were similar if not higher than these observed following IV dosing. Tissue levels two hours after administration ranged from ~335 – 425 nM compared to 90 nM in blood (Table 2). Assuming an elimination half-life of ~10h, tissue levels most likely exceeded 50-100 nM for >24h.

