3.5.2 Monitoring During Treatment

- Physical exam, to include vital signs, weight, toxicity evaluation and ECOG status within 4 days of each treatment cycle.

- Laboratory Evaluations (Days 1-5 while hospitalized, unless otherwise indicated below*):
 - CBC with differential count.
 - Chemistry: sodium, potassium, chloride, CO₂, creatinine, glucose, BUN, albumin, ionized calcium**, magnesium, alkaline phosphatase, ALT/GPT, AST/GOT, total bilirubin, total protein.
 - Total and fractionated serum bile acids on Day 1 (prior to infusion) and Day 5 of Cycle 1 (+/- 3 days) and at treatment evaluation.
 - Coagulation Studies: PT/PTT/Thrombin Time, Fibrinogen.
Note: The patient may have evaluations and lab work obtained through his or her local physician in between treatments and have the results faxed to the Research Nurse. The Research RN will contact the patient as noted above to discuss toxicity.

*** Note:** Day 1 labs can be drawn on the day prior to infusion. In between treatments, the above labs may be drawn twice weekly (+48 hours between labs). For patients not experiencing Grade 3 or 4 toxicities these labs may be drawn once weekly in between treatments per PI discretion instead.

**** Ionized calcium** is not part of a standard lab panel and may be omitted if not available or not covered by insurance when performed outside NIH. 12-Lead EKG:
 - Cycle 1: Days 1 (within 2 hours prior to infusion), 2 (within 2 hours post-infusion), 3, 4 and 5, to evaluate for QT prolongation potential.
Note: EKGs may be done outside of the specified times if unexpected events in clinic prevent staff from conducting the study within the specified timeframe. EKGs performed outside of this window will NOT be considered protocol deviations.
 - Cycle 2 and subsequent cycles: within 2 hours prior to start and within 2 hours following completion of infusion.
- Ultrasonic liver elastography Day 4 of Cycle 1 (+/- 3 days) and Day 1 (+/- 3 days) of subsequent cycles and at treatment evaluation.

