10.3 SECONDARY ENDPOINTS

Pharmacokinetic analysis will be conducted using non-compartmental methods. For pharmacodynamic endpoints, descriptive statistics will be used for each endpoint. Briefly, pharmacokinetics and molecular endpoints in target tissues will be assessed before and after mithramycin treatment, with the primary focus being comparison of microarray, qRT-PCR and IHC results relative to profiles identified in our preclinical studies. It is anticipated that non-parametric statistical methods will be used to compare paired results before and after treatment (but not between groups), as well as to perform comparisons or correlations among parameters. As the exact set of comparisons and analyses to be performed will be determined following

completion of the trials, and will be based on limited numbers of patients, the analyses will be considered exploratory and hypothesis generating rather than definitive. The results of these descriptive analyses will be used to design further studies.

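### Cycle 1 PK sampling ends about one stated half-life after the infusion, too early for a reliable terminal half-life if the 10.6 h figure is right

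*Combined protocol and SAP*

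**What the plan says.** Section 1.1.1 makes pharmacokinetics part of the first primary objective: "To determine pharmacokinetics, toxicities, and maximum tolerated dose (MTD) of mithramycin administered as a continuous 24h infusion". The analysis is described in Section 10.3, under secondary endpoints: "Pharmacokinetic analysis will be conducted using non-compartmental methods". No parameters are listed, and there is no terminal-phase rule or limit on extrapolated AUC.

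The Cycle 1 worksheet (Appendix 3, Section 14.3.3.1) takes a pre-dose sample, samples at 2, 8 and 16 h, and one "Just prior to the end of the 24 hour infusion". After the infusion it samples at 0.25, 0.5, 1, 2, 3 and 5 h, then "7h post infusion", and last at "9-12h post infusion". Cycles 2 to 4 have only a pre-dose and an end-of-infusion sample.

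Section 1.3.2.1 gives the only human elimination data: biphasic decline and a "mean elimination half-life of 10.6 hours (±1.7" in three patients, by radioimmunoassay after 2 h infusions, labelled preliminary. The same section uses about 10 h in its own reasoning and reports 5 h in monkeys.

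Section 3.5.2 already schedules Cycle 1 laboratory bloods on "Days 1-5 while hospitalized" and EKGs on Days 3, 4 and 5.

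**The concern.** A non-compartmental half-life is a regression slope through the last few log concentrations. AUC to infinity is the observed area plus the last concentration divided by that slope; clearance is dose over that AUC, and volume uses the slope again. All of them need the terminal phase to be seen. With biphasic elimination and a 10.6 h half-life, a record that stops 9-12 h after the infusion sees little of it, and part of what it sees may still be the early phase. The next pre-dose sample comes about 13 days after the infusion ends and cannot help.

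Section 3.1.2.1 bases the dose levels on PK modelling, and the notes to Figure 7 say that earlier concentrations were lower than predicted. The PK from this trial is therefore the natural check on that model.

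**Working it through.** The plan states no PK precision target, so there is no figure of its own to reproduce.

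**Inputs from the documents:** 24 h infusion; last sample T = 9 to 12 h after its end; half-life h = 10.6 h, with 8.9-12.3 h for ±1.7 and 5 h from monkeys. **Assumed:** 10% random error in each concentration.

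**1. Coverage, T/h.** 9/10.6 = 0.85 and 12/10.6 = 1.13 half-lives. Counting from the 3 h sample: 6/10.6 = 0.57 to 9/10.6 = 0.85.

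**2. Extrapolated share of AUC, one compartment.** With k = ln2/h, the share is (1 − e^(−24k))·e^(−kT)/(24k).

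| h | T = 9 h | T = 12 h | T = 24 h | T = 48 h |
|---|---|---|---|---|
| 5 h | 8.3% | 5.5% | 1.0% | 0.0% |
| 8.9 h | 22.4% | 17.8% | 7.0% | 1.1% |
| 10.6 h | 28.0% | 23.0% | 10.5% | 2.2% |
| 12.3 h | 33.0% | 27.9% | 14.2% | 3.7% |

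**3. Precision of the slope at h = 10.6 h.** CV = 0.10/(k·√Sxx), with k = 0.0654 per hour and Sxx the sum of squared deviations of the sampling times.
- 3, 5, 7 and 10.5 h: Sxx = 30.7, CV = 27.6%.
- All eight post-infusion samples, valid only if decline is single-phase: Sxx = 91.6, CV = 16.0%.
- 3 to 10.5 h plus 24 h: Sxx = 279, CV = 9.2%.
- Plus 24 and 48 h: Sxx = 1,489, CV = 4.0%.

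**4. Simulated non-compartmental analysis on the Appendix 3 times.** The true terminal half-life is 10.6 h and the slope is taken from 3 h onward. With one phase, the 5th-95th percentiles of estimated half-life are 6.8-23.3 h (last sample 9 h) or 7.6-16.8 h (12 h). Assuming a first phase of 1-2 h that carries 30-50% of AUC, the error-free estimate is biased down to 5.7-9.5 h. Clearance does better: error-free bias is +1% to +8%, and the 5th-95th percentiles are 0.70-1.16 of true at worst (one phase, 9 h) and 0.84-1.12 with a 12 h sample. With added 24 h and 48 h samples, half-life is within about 9.4-11.6 h across all the scenarios.

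**5. How firm is 10.6 h?** Section 1.3.2.1 also gives a clearance of 11.1 mL/min/m². For 70 kg and 1.8 m² (assumed), a 6 h infusion of 25 mcg/kg runs at 25×70/6 = 291.7 mcg/h, and clearance is 1.20 L/h. The predicted end level is 291.7/1.20 × (1 − e^(−6k)) = 79 ng/mL. At 1.085 ng/mL per nM (Table 2) that is about 73 nM. Section 1.3.4.1 reports a peak of 20 nM, so the two published parameters do not both fit the later trial.

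A rough effective half-life comes from comparing end-of-infusion level per unit dose, 24 h against 6 h: [(1 − e^(−24k))/24]/[(1 − e^(−6k))/6]. Using 20 nM (Section 1.3.4.1) and the projected 50-100 nM at 210-350 mcg/kg (Section 3.1.2.1):
- (50/210)/(20/25) = 0.298, which solves to h = 2.3 h.
- (100/350)/(20/30) = 0.429, which solves to h = 5.0 h.

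This ignores carry-over between daily infusions, relies on a projection, and does not exclude a long, low terminal phase.

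**The case against.** The 10.6 h rests on three patients and an older assay. The sponsor has since measured 12 patients over 20 cycles and has early results from this trial. The text of Section 1.3.4.2 and Figures 7, 10 and 11 were not available to read, and the half-life the sponsor designed around may be there. The visible levels point to something shorter; at 5 h or less the schedule extrapolates at most about 8% of AUC. The 28% slope CV also discards the early samples, and the 10% error is assumed. No section names half-life or clearance as required, and the stated exposure target, the level at the end of infusion, is sampled directly.

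Most of this stands and limits the point. What remains is that the schedule is adequate only if the half-life is well below the protocol's own human figure, and it cannot readily tell. In the 2 h first-phase scenario a true 10.6 h terminal half-life is estimated, without error, as 5.7 h, close to the reassuring 5 h. The extrapolated share is then reported as 9.0%, when it is about 0.5 × 28.0% = 14%.

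A reader might infer that clearance cannot be obtained at all. The documents do not support that: at 10.6 h sampling captures 72-77% of AUC, and the end-of-infusion level is already 1 − e^(−24k) = 79% of steady state.

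**Conclusion.** The point holds conditionally. If the terminal half-life is near 10.6 h, the planned samples give an unreliable individual half-life and derived volume: slope CV is about 28%, or 16% on the more favourable single-phase reading, with 10% error assumed. AUC to infinity and clearance are then moderately uncertain, with 23-28% of AUC extrapolated (18-33% over 8.9-12.3 h). If the half-life is 5 h or less, the schedule is largely adequate. End-of-infusion levels and AUC to the last sample are sound in either case, and the Phase II response analysis is unaffected. Confidence is moderate, because the sponsor's later PK data could not be seen. A late sample is worth adding because it would settle the question: in a single-phase decline, the level 24 h after infusion is 2^(−24/10.6) = 21% of the end-of-infusion level at 10.6 h, but 2^(−24/5) = 4% at 5 h.

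**What to change.** In Appendix 3, add one timed Cycle 1 PK sample about 24 h after the infusion ends (Day 3), with the actual time recorded. At 10.6 h this cuts extrapolated AUC to 10.5% and slope CV to about 9%. A sample at about 48 h (Day 4) is optional. It needs a fixed time, since the Day 4 research blood has a ±3-day window, and it is useful only if the assay can measure it.

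In Section 10.3, name the PK parameters. State that half-life, clearance and AUC to infinity are reported only when extrapolated AUC is below a set limit, for example 20%; otherwise report AUC to the last sample. This rule does not replace the late sample, because a half-life biased short also makes the extrapolated share look small.

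The cost is one or two extra 6 mL samples and assays per patient, with no new visit. Appendix 3 requires PK blood to be drawn away from the infusion line, so a separate venous stick may be needed. Scaling Section 3.1.2.1 to 30-45 mcg/kg gives about 7-13 nM at the end of infusion (30 × 50/210 to 45 × 100/350). At 10.6 h that leaves about 1.5-2.7 nM at 24 h and 0.3-0.6 nM at 48 h. The assay limit is not stated, so the later sample in particular may be unmeasurable. If the sponsor's existing data already establish a short terminal half-life, citing them in Section 10.3 would answer the point without extra blood.

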14.3.3.5 Instructions

PK Studies (PK)

Collect 6 mL blood in 2 lavender top (3 mL) tubes. Blood has to be drawn from a site away from the site of infusion (cannot be drawn through the line used to infuse drug, or through another lumen of that line). Following blood collection, the tubes should be inverted several times to ensure mixing with the anticoagulant. Tubes should then be placed on crushed ice, and samples should be centrifuged for 15 minutes at approximately 1000 x g at 0-5 °C within 2 hours after collection. The plasma should be transferred to separate pre-labeled screw-capped polypropylene transfer tubes and stored at -80 °C until sent to the analytical site ([name] Lab).

Research Labs (R)

Samples will be collected in 2 red top (10 mL) and 2 lavender top (10 mL) tubes for PD studies and PBMC, and transported on wet ice within 1 hour to the Thoracic Epigenetics Lab (TEL).

Research Labs will be collected at the following timepoints (see also [Appendix 2: Study Calendar](#)):

- Baseline (once), see Section [3.5.1](#);
- Within 72 h **prior to starting each infusion cycle**;
- Day 4 of Cycle 1 (+/- 3 days); and at
- Treatment evaluation.

Coagulation Studies (C)

One blue top tube transported to the TEL lab within 1 hour. Samples (1 mL of plasma) will be obtained, filtered through a 22 micron filter (Kit available in TEL) and stored at -80° C, to be saved for future clinical reference as needed.

Labeling

Prior to the infusion, the PK /research lab sheet and labels will be placed in the patient's room and a separate set of labels will be given to the Thoracic Epigenetics Lab staff. The labels will list the patient identifiers and either "Cycle 1" or "Cycle 2" as appropriate. As the RN (or designee) draws the bloods, the RN (or designee) will place a label on the tube and write the sample reference # on the label on the tube. When the Thoracic Epigenetics Lab personnel or fellow processes the sample, the TEL personnel will label the storage tube with the label and will transcribe the corresponding sample reference # on the label on the tube.

Tracking

Upon completion of the PK/Research sample draws, the research nurse will make 3 copies of the PK sheet. The original and one copy should be placed in the research binder. 2 copies should be given to the TEL personnel. TEL will retain one copy for their records and

Abbreviated Title: 24 h Mithramycin Infusion
Version Date: 12/22/2020

will send the other copy with the PK samples to the [name] Lab. **Note:** Prior to sending the PK sheets to the [name] Lab, the patient name should be crossed out.

14.3.4 Appendix 4: Sample Patient Log for Reactions/Symptoms

NAME: _____ Cycle: _____

Dates of last Mithramycin infusion: _____

Reaction/Symptom	Start Date	End Date

*Contact your study center team or local physician right away if you experience signs of bleeding. This may include, but is not limited to, petechiae (red or purple spots on the skin), nosebleeds; bruising; or blood in urine, stool or vomit.

Patient signature: _____ Date: _____

Reviewed by: _____ RN/MD Date: _____

14.3.5 Appendix 5: Sample Patient Log for Concomitant Medication

NAME: _____ Cycle: _____

Dates of last Mithramycin infusion: _____

Medication Taken	Start Date	End Date

*Contact your study center team or local physician right away if you experience signs of bleeding. This may include, but is not limited to, petechiae (red or purple spots on the skin), nosebleeds; bruising; or blood in urine, stool or vomit.

Patient signature: _____ Date: _____

Reviewed by: _____ RN/MD Date: _____

14.3.6 Appendix 6: Sample Monitoring Toxicities Between Mithramycin Cycles with Local Physician

Patient Name: _____

Dates and Doses of last Mithramycin: _____ Cycle: _____

Dear Dr. _____,

The patient named above is currently participating on a Phase I/II Mithramycin study at the National Cancer Institute at the National Institutes of Health in Bethesda, Maryland, and requires the following lab tests and evaluations between _____ and _____:

(date) (date)

- History, physical exam: Once Weekly
- Weight: Once Weekly
- Labs: (Circle one) Twice Weekly during Cycles 1-3 or Once Weekly after Cycle 3.
 - **CBC/Diff**
 - **Chemistry Panel** (include sodium, potassium, chloride, CO₂, creatinine, glucose, BUN, albumin, calcium, magnesium, LDH, phosphorus, uric acid)
 - **LFT** (include alk phos, ALT/AST, Total bilirubin, Direct bilirubin, Total protein)
 - **Coagulation profiles** – PT/PTT, fibrinogen

Please FAX all lab results and medical summaries to [name], M.D. or [name], R.N. at [contact].

For any questions, please call [contact] or [contact], or email [contact]

For urgent issues, contact the Attending Physician or [name] through the NIH Operator at [contact].

***If the patient experiences any signs of bleeding (≤ Grade 2) including, epistaxis, hematuria, hematemesis or blood in the stool, the patient will require immediate comprehensive clinical evaluation and coagulation profile (including PT/PTT/fibrinogen, thrombin time, PFA-100, D-dimer, Ca²⁺ and ionized calcium).**

Please contact the NIH page operator at [contact] and ask for the Thoracic Surgery Attending Physician on call or [name] with any clinically significant bleed and support with appropriate blood product support. Bleeding that does not stop within 6 hours with appropriate treatment will be considered a dose limiting toxicity and further dosing of mithramycin will be discontinued.

Physician Signature

NIH/NCI/TSB

Print Name
